### **Administration of Additional Treatment Cycles:**

Subjects may discontinue treatment due to disease progression, unacceptable AEs, or at the subject's request. Treatment decisions related to subject management will be based exclusively on RECIST version 1.1 or the Lugano 2014 criteria, or PCWG3 criteria (including PSA assessments). Subjects with an objective response of CR, partial response (PR) or stable disease, will continue therapy until they develop progressive disease (PD, unless in case of treatment beyond progression), experience clinical deterioration, develop AEs requiring discontinuation of treatment or withdraw consent.

Subjects who develop toxicity requiring discontinuation of treatment will enter the Clinical Follow-up Period. The subject should be seen in follow-up at least every 30 days, until the AE has resolved to baseline, stabilized, or been deemed irreversible. After completion of the Clinical Follow-up Period, subjects will then enter the Survival Follow-up Period. [REDACTED]

The overall duration of the study is expected to be approximately 6 years from the time of the first visit of the first subject to the required survival follow-up of the last subject enrolled. Subjects may discontinue treatment due to disease progression, unacceptable AEs, or withdrawal of consent. The Clinical Follow-up visits will occur approximately 30 days (for subjects who receive monotherapy) after the subject discontinues study treatment. For subjects in PR or CR who discontinue treatment for AEs, tumor assessments will be performed every 12 weeks for the first year then every 6 months for the second year. If a subject discontinues treatment due to an AE, the subject should be seen in Clinical Follow-up every 30 days until the AEs either resolved to baseline or Grade 1, stabilized, or been deemed irreversible. After completing the Clinical Follow-up Period, subjects will continue on to a Survival Follow-up Period. [REDACTED]

[REDACTED] The end of the study will occur after the last treated subject completes their Clinical Follow-up, unless a subject discontinues prematurely. Subjects in Survival Follow-up Period who have progression of disease will be eligible to receive anticancer therapy as appropriate.

## **2.2 Treatment Assignment**

This is an open-label study. Enrolled subjects, including those not dosed, will be assigned sequential subject numbers starting with 00001, eg, 00001, 00002, 00003.... 00010. Those enrolled subjects meeting eligibility criteria will be eligible to be dosed. Sequential numbering may restart

at 00001 for each participating site as the distinct subject identification number (PID) will ultimately be comprised of the site number and subject number, eg, 0002 00001.

During Part 1, once informed consent has been obtained, the investigator (or designee) will register the subject by transmitting a copy of the completed enrollment worksheet (registration form) to the Sponsor. Treatment groups and/or dose levels will be provided to the site study team after the subject has registered and eligibility for the study confirmed.

In Part 2, during the screening visit, the investigative site will call into the enrollment option of the interactive response technology (IRT) designated by BMS. Enrolled participants, including those not dosed, will be assigned sequential participant numbers for their site starting with 00001, (eg, 00001, 00002, 00003.... 00010). The patient identification number (PID) will ultimately be comprised of the site number and participant number. Once it is determined that the participant meets the eligibility criteria following the screening visit, the investigative site will call the IRT to centrally assign the participant into the appropriate monotherapy cohort.

### 2.3 Blinding and Unblinding

This study is a non-randomized open-label study for Part 1 and Part 2. Interactive Response Technology (IRT) will be used in Part 2 for treatment assignment. Data emerging from this exploratory study may be necessary to inform timely decisions for adjusting procedures in subsequent portions of the study, including early termination of the study. Additionally, availability of the open label treatment assignments may facilitate optimization of the bioanalytical analysis of samples.

### 2.4 Protocol Amendments

This SAP incorporates the following protocol amendments (Table 2.4-1).

**Table 2.4-1: Protocol Amendments**

Document	Date of Issue	Summary of Major Changes
Amendment 01	10-Aug-2015	Revisions to Inclusion/Exclusion criteria, T&E table, and minor typographical edits
Amendment 04	03-Mar-2016	Incorporates new dosing regimens, revisions to the inclusion/exclusion criteria, T&E table and minor typographical edits
Amendment 05	12-Apr-2016	Removes Parts 1B & 2B and pertaining language from the protocol; incorporates revisions to the inclusion/exclusion criteria, T&E table, and minor typographical edits.
Revised Protocol 04	06-Sep-2017	Adds nivolumab to Part 2 escalation phase and updates to biomarker driven study design with additional tumor types added. Includes revisions to rationales, inclusion/exclusion criteria, T&E table, sample collection tables and statistics; and minor typographical edits.
Revised Protocol 05	01-Mar-2018	Incorporates Administrative Letter 04 and the following changes: 1) clarify the acceptable prior lines of therapy for participants with Non-Small Cell Lung Cancer (NSCLC) in Part 2; 2) update Exclusion Criteria for subjects participating in Part

**Table 2.4-1: Protocol Amendments**

		2; and 3) provide updated contraception and protection requirements based on recent non-clinical reproductive toxicology study. Study design elements including time and events schedules, sample collections, laboratory analyses and additional safety measures have been added to align with these changes.
Revised Protocol 06	17-Jul-2018	Updates schedules for mandatory biopsies during Part 2, updates imaging requirements for tumor assessments; updates inclusion criteria for subjects with NSCLC, corrects dose-limiting toxicity period for Part 2, updates schedules for PK sample collections, includes language to allow for release of IRT codes to facilitate ongoing data review, and added PROSTATE CANCER WORKING GROUP 3 (PCWG3) appendix.
Revised Protocol 07	18-Mar-2019	Identifies the dose and schedule for Part 2 and updates the study design for Part 2. Includes revisions to rationales, inclusion/exclusion criteria, T&E tables, sample collection tables and statistics; minor typographical edits, and an update to Appendix 4 RECIST 1.1. [REDACTED]

[figure not shown]
### 3 OBJECTIVES

#### 3.1 Primary

- To assess the safety and tolerability and to assess the DLTs, MTD, and recommended Phase 2 dose (RP2D) of BMS-986158 as monotherapy for subjects with advanced solid tumors and hematologic malignancies

#### 3.2 Secondary

- To assess the preliminary anti-tumor activity of BMS-986158 monotherapy as measured by ORR, and response duration based on response evaluation criteria in solid tumors (RECIST) v1.1, prostate cancers using PCWG3 criteria, or hematologic malignancies using criteria from Lugano 2014.
- To characterize PK of BMS-986158 and metabolite in monotherapy.
- To assess the dose-response and exposure-response effect of BMS-986158 monotherapy on the ECG (QT interval).

## 4 ENDPOINTS

### 4.1 Safety Endpoint(s)

The assessment of safety will be based on the incidence of adverse events (AEs), serious adverse events (SAEs), adverse events leading to discontinuation, deaths and frequency of laboratory test toxicity grade shifting from baseline.

Toxicities will be graded using the National Cancer Institute (NCI) Common Terminology Criteria for Adverse Events (CTCAE) version 4.03 in the first 32-35 days of dosing (DLT evaluation period for Schedule A) and in the first 35 days of dosing (DLT evaluation period for Schedules B and C).

### 4.2 Secondary Endpoints

Secondary endpoints comprise preliminary antitumor activity, PK, and electrocardiogram (ECG) results and are described below.

#### 4.2.1 Preliminary Antitumor Activity

Changes in solid tumor measurements and tumor response will be assessed by the RECIST v1.1 (Response Evaluation Criteria in Solid Tumors version 1.1) (Protocol Appendix 4), or PCWG3 for prostate cancer (Protocol Appendix 12). PCWG3 criteria is intended for Part 2 subjects and not Part 1 subjects. Changes in hematologic malignancies will be assessed using Lugano 2014 criteria (Protocol Appendix 9). In Schedule A (Part 1), tumor assessments will occur 8 weeks ( $\pm 1$  week) after treatment begins and continue every 8 weeks ( $\pm 1$  week) until investigator-assessed disease progression or treatment discontinuation. In Schedules B and C (Part 1), tumor assessments will occur 9 weeks ( $\pm 1$  week) after treatment begins and continue every 9 weeks ( $\pm 1$  week) until investigator-assessed disease progression or treatment discontinuation. In Part 2, Schedule A, tumor assessments will occur 8 weeks ( $\pm 1$  week) after treatment begins and continue every 8 ( $\pm 1$  week) until investigator-assessed disease progression or treatment discontinuation.

The following set of study-level efficacy endpoints will be used.

- Objective Response Rate (ORR): defined as the total number of subjects whose best overall response (BOR) is either a CR or PR divided by the total number of subjects in the population of interest.
  - Best overall response (BOR): defined as the best response designation recorded between the dates of first dose and the date of first objectively documented progression per Investigator assessed RECIST v1.1 (or Lugano 2014 criteria for hematologic malignancies or PCWG3 for prostate cancer) or the date of subsequent therapy, whichever occurs first.

Investigator reported CR or PR was not always confirmed by a second scan. Therefore, ORR summaries will be presented regardless of confirmation. For subjects without documented progression or subsequent therapy, all available response designations will contribute to the BOR assessment. For subjects who continue treatment beyond progression or begin subsequent therapy, the BOR should be determined based on response designations recorded up to the time of the initial RECIST v1.1 (or by Lugano 2014 criteria for hematologic malignancies, or PCWG3 criteria for prostate cancer [CRPC or NEPC]) defined progression or subsequent therapy, whichever occurs first. For those subjects who have surgical resection, only pre-surgical tumor assessments will be considered in the determination of BOR.

- Duration of Response (DOR): defined as the time between the date of first response (CR or PR) and the date of the first objectively documented disease progression (as determined using RECIST v1.1 for solid tumors, Lugano 2014 criteria for hematologic malignancies, or PCWG3 (including PSA assessments) for prostate cancer [CRPC or NEPC]), or death due to any cause, whichever occurs first. For those subjects who remain alive and have not progressed, duration of response will be censored on the date of last evaluable tumor assessment. Subjects who started subsequent therapy without a prior reported progression will be censored at the last evaluable tumor assessment prior to initiation of the subsequent anticancer therapy. Response duration will only be evaluated in subjects with a BOR of CR or PR. Duration of response will be reported if there are more than 5 CR or PR in a tumor type
- Progression Free Survival (PFS): defined as the time from the first dose of study medication to the date of the first objective documentation of tumor progression or death due to any cause. Clinical deterioration in the absence of radiographic evidence is not considered progression for the purpose of determining PFS. Subjects who neither progressed nor died will be censored on the date of their last evaluable tumor assessment. Subjects who did not have any evaluable on-study tumor assessments will be censored on the date of the first dose of study medication. Subjects who started subsequent therapy without a prior reported progression will be censored at the last evaluable tumor assessment prior to initiation of the subsequent anticancer therapy.
- Progression Free Survival Rate (PFSR) at week 't': defined as the proportion of subjects who remain progression free and surviving at 't' weeks (t=12, 24). The proportion will be calculated by the product-limit method (Kaplan-Meier estimate) which takes into account censored data.

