8.3.2.1 Efficacy

The first secondary objective (efficacy) will be based on RECIST v1.1 for solid tumors (Appendix 4), Lugano 2014 criteria for hematologic malignancies (Appendix 9), or PCWG3

```
Revised Protocol No.: 07
Date: 18-Mar-2019
```

criteria for prostate cancer (CRPC or NEPC) (Appendix 12) using the following secondary endpoints:

- Best overall response (BOR): defined as the best response designation, recorded between the dates of first dose and the date of first objectively documented progression (per RECIST v1.1 for solid tumors, Lugano 2014 criteria for hematologic malignancies or PCWG3 for prostate cancer) or the date of subsequent therapy, whichever occurs first. CR or PR determinations included in the BOR for solid tumor assessments must be confirmed by a second scan performed no less than 4 weeks, and for hematologic malignancies, no less than 2 weeks after the criteria for response are first met. For subjects without documented progression or subsequent therapy, all available response designations will contribute to the BOR assessment. For subjects who continue treatment beyond progression or begin subsequent therapy, the BOR should be determined based on response designations recorded up to the time of the initial evaluation (RECIST v1.1 for solid tumors, Lugano 2014 criteria for hematologic malignancies or PCWG3 criteria for prostate cancer [CRPC or NEPC]) defined progression or subsequent therapy, whichever occurs first. For those subjects who have surgical resection, only presurgical tumor assessments will be considered in the determination of BOR. A BOR of SD requires a minimum of 49 days on study from date of first dose to the date of the first imaging assessment.
- ORR: defined as the total number of subjects whose BOR is either a CR or PR divided by the total number of subjects in the population of interest

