- Duration of Response (DOR): defined for a subject with confirmed response as the time between the date of first response and the date of the first objectively documented disease progression (as determined by RECIST v1.1 for solid tumors, Lugano 2014 criteria for hematologic malignancies, or PCWG3 (including PSA assessments) for prostate cancer [CRPC or NEPC]), or death due to any cause, whichever occurs first. For those subjects who remain alive and have not progressed, duration of response will be censored on the date of last tumor assessment. Subjects who started subsequent therapy without a prior reported progression will be censored at the last tumor assessment prior to initiation of the subsequent anticancer therapy. Response duration will only be evaluated in subjects with a BOR of CR or PR.
- PFS: defined as the time from the first dose of study medication to the date of the first objective documentation of tumor progression or death due to any cause. Clinical deterioration in the absence of radiographic evidence is not considered progression for the purpose of determining PFS. Subjects who neither progressed nor died will be censored on the date of their last tumor assessment. Subjects who did not have any on-study tumor assessments will be censored on the date of the first dose of study medication. Subjects who started subsequent therapy without a prior reported progression will be censored at the last tumor assessment prior to initiation of the subsequent anticancer therapy.
- Progression Free Survival Rate (PFSR) at week 't' : defined as the proportion of subjects who remain progression free and surviving at 't' weeks (t=12, 24). The proportion will be calculated by the product-limit method (Kaplan-Meier estimate) which takes into account censored data.

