2.3.3 Best Overall Response

Best response determination of complete or partial response requires confirmation: Complete or partial responses may be claimed only if the criteria for each are met at a subsequent time point of \geq 4 weeks (28 days) later. In this circumstance, the best overall response can be interpreted as in Table 2.3.3-1. When SD is believed to be best response, it must meet the protocol specified minimum time from the date of first treatment or randomization date.

For example, if the first scheduled follow-up imaging visit is Week 6 (\pm 7 days) for a particular protocol, a Best Response of SD can only be made after the subject is on-study for a minimum of 6 weeks (42 days) minus 7 days, for an absolute minimum time on-study of 35 days from the reference start date (reference date is considered Day 1 on study). If the subject is not on-study for at least this amount of time, any tumor assessment indicating stable disease before this time period will have a Best Response of NE unless PD is identified.

Special note on response assessment: When nodal disease is included in the sum of target lesions and the nodes decrease to 'normal' size (< 10 mm), they may still have a measurement reported on scans. This measurement should be recorded even though the nodes are normal in order not to overstate progression should it be based on increase in size of the nodes. As noted earlier, this means that patients with CR may not have a total sum of 'zero' on the case report form (CRF).

Table 2.3.3-1:	Best Overall Response (Confirmation of CR and PR Required)	
Overall Response First Time Point	Overall Response Subsequent Time Point	Best Overall Response
CR	CR	CR
CR	PR	SD, PD OR PR ^a
CR	SD	SD provided minimum criteria for SD duration met, otherwise, PD
CR	PD	SD provided minimum criteria for SD duration met, otherwise, PD
CR	NE	SD provided minimum criteria for SD duration met, otherwise, NE

Table 2.3.3-1:	Best Overall Response (Confirmation of CR and PR Required)	
Overall Response First Time Point	Overall Response Subsequent Time Point	Best Overall Response
PR	CR	PR
PR	PR	PR
PR	SD	SD
PR	PD	SD provided minimum criteria for SD duration met, otherwise, PD
PR	NE	SD provided minimum criteria for SD duration met, otherwise, NE
NE	NE	NE
CR = complete response, PR = partial response, SD = stable disease, PD = progressive disease, and		
NE = inevaluable		

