2.3.4 Confirmation Scans

Verification of Response: To be assigned a status of CR or PR, changes in tumor measurements must be confirmed by consecutive or subsequent repeat assessments that should be performed no less than 28 days after the criteria for response are first met. Subsequent documentation of a CR may provide confirmation of a previously identified CR even with an intervening NE or PR (eg, CR NE CR or CR PR CR). Subsequent documentation of a PR may provide confirmation of a previously identified PR even with an intervening NE or SD (eg, PR NE PR or PR SD PR). However, only one (1) intervening time point will be allowed between PR/CRs for confirmation.

Verification of Progression: Progression of disease should be verified in cases where progression is equivocal. If repeat scans confirm PD, then progression should be declared using the date of the initial scan. If repeat scans do not confirm PD, then the subject is considered to not have progressive disease.

REFERENCES

¹ Eisenhauer EA, Therasse P, Bogaerts J, et al. New response evaluation criteria in solid tumors: revised RECIST guideline (version 1.1). Eur J Cancer 2009; 45: 228-47.

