2.3.3 Best Overall Response

Best response determination of complete or partial response requires confirmation: Complete or partial responses may be claimed only if the criteria for each are met at a subsequent time point of \geq 4 weeks (28 days) later. In this circumstance, the best overall response can be interpreted as in Table 2.3.3-1. When SD is believed to be best response, it must meet the protocol specified minimum time from the date of first treatment or randomization date.

For example, if the first scheduled follow-up imaging visit is Week 6 (\pm 7 days) for a particular protocol, a Best Response of SD can only be made after the subject is on-study for a minimum of 6 weeks (42 days) minus 7 days, for an absolute minimum time on-study of 35 days from the reference start date (reference date is considered Day 1 on study). If the subject is not on-study for at least this amount of time, any tumor assessment indicating stable disease before this time period will have a Best Response of NE unless PD is identified.

Special note on response assessment: When nodal disease is included in the sum of target lesions and the nodes decrease to 'normal' size (< 10 mm), they may still have a measurement reported on scans. This measurement should be recorded even though the nodes are normal in order not to overstate progression should it be based on increase in size of the nodes. As noted earlier, this means that patients with CR may not have a total sum of 'zero' on the case report form (CRF).

Table 2.3.3-1:	Best Overall Response (Confirmation of CR&PR Required)				
Overall Response First Time Point	Overall Response Subsequent Time Point	BEST Overall Response			
CR	CR	CR			
CR	PR	SD, PD OR PR ^a			
CR	SD	SD provided minimum criteria for SD duration met, otherwise, PD			
CR	PD	SD provided minimum criteria for SD duration met, otherwise, PD			
CR	NE	SD provided minimum criteria for SD duration met, otherwise, NE			
PR	CR	PR			
PR	PR	PR			
PR	SD	SD			
PR	PD	SD provided minimum criteria for SD duration met, otherwise, PD			
PR	NE	SD provided minimum criteria for SD duration met, otherwise, NE			
NE	NE	NE			

Revised Protocol No.: 07 Date: 18-Mar-2019

Table 2.3.3-1:	Best Overall Response (Confirmation of CR&PR Required)	
Overall Response First Time Point	Overall ResponseBEST Overall ResponseSubsequent Time Point	
CR = complete response, PR = partial response, SD = stable disease, PD = progressive disease, and		
NE = inevaluable		

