2.3.4 Confirmation Scans

Verification of Response: To be assigned a status of CR or PR, changes in tumor measurements must be confirmed by consecutive or subsequent repeat assessments that should be performed no less than 28 days after the criteria for response are first met. Subsequent documentation of a CR may provide confirmation of a previously identified CR even with an intervening NE or PR (eg, CR NE CR or CR PR CR). Subsequent documentation of a PR may provide confirmation of a previously identified PR even with an intervening NE or SD (eg, PR NE PR or PR SD PR). However, only one (1) intervening time point will be allowed between PR/CRs for confirmation.

Verification of Progression: Progression of disease should be verified in cases where progression is equivocal. If repeat scans confirm PD, then progression should be declared using the date of the initial scan. If repeat scans do not confirm PD, then the subject is considered to not have progressive disease.

REFERENCES

¹ Trial Design and Objectives for Castration-Resistant Prostate Cancer: Updated Recommendations From the Prostate Cancer Clinical Trials Working Group 3. Scher et al. J Clin Oncol 2016, 34(12):1402-1418

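### The SAP reports ORR without requiring confirmed response, against protocol 8.3.2.1, with no confirmed ORR planned and the departure not flagged

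*SAP*

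**What the plan says.** Protocol 8.3.2.1, on best overall response (BOR): "CR or PR determinations included in the BOR for solid tumor assessments must be confirmed by a second scan performed no less than 4 weeks" later. The corresponding minimum interval in hematologic disease is 2 weeks. The same section defines ORR as the share of subjects whose BOR is CR or PR, so ORR inherits the confirmation requirement. Duration of response (DOR) is "defined for a subject with confirmed response as the time between the date of first response".

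The response appendices agree. Appendix 4 (RECIST 1.1), section 2.3.3: "Best response determination of complete or partial response requires confirmation"; section 2.3.4: "To be assigned a status of CR or PR, changes in tumor measurements must be confirmed by consecutive or subsequent repeat assessments". Appendix 12 (PCWG3), section 2.3.3: "Complete or partial responses may be claimed only if the criteria for each are met at a subsequent time point"; section 2.3.4 adds that the repeat assessments are ones "that should be performed no less than 28 days after the criteria for response are first met". SAP 4.2.1 names both appendices as the basis for response assessment.

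SAP 4.2.1, repeated in 7.5: "Investigator reported CR or PR was not always confirmed by a second scan. Therefore, ORR summaries will be presented regardless of confirmation".

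The ORR entry in the SAP 7.5 summary list gives ORR with a Clopper-Pearson interval and the BOR categories. No confirmed version is listed. SAP 9 refers to a separate Data Presentation Plan for table mock-ups.

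On DOR, SAP 4.2.1 drops the confirmed-response condition and reports DOR when a tumor type has more than five CR or PR. SAP 7.5 states the same threshold in terms of confirmed responses, as an example in the summary list and as a rule in the figure list.

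**The concern.** The two documents define one endpoint in two ways. SAP section 1 says that the SAP supersedes the protocol's statistical considerations, so the SAP version is the one that will be reported. The same section undertakes to identify substantial differences from the protocol. SAP 4.2.2 does so for the pharmacokinetic parameters, with explicit reference to the protocol. Nothing comparable is said for ORR, and the SAP document history does not mention it. A reader learns that unconfirmed responses count, but not that the protocol excludes them.

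The SAP's reason, that confirmation was sometimes missing, describes a case the protocol already covers. Table 2.3.3-1 of Appendices 4 and 12 moves a response that is not confirmed at the next assessment to SD, PD or NE, depending on that assessment and the time on study. (A claimed CR followed by PR may also be reclassified as PR.) No new rule was needed.

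Two things are at stake: whether the reported ORR is the protocol's secondary endpoint, and which count is held against the two-stage boundaries. SAP 5.2 speaks only of subjects who respond to therapy and does not say whether the response must be confirmed.

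**Working it through.** **1. The plan's own figures.** SAP Table 5.2-1 uses 5 subjects in stage 1 and 9 in total. A cohort is futile at 0 of 5. It succeeds with at least 3 of 9 (target 50% against 10%; stated FPR/FNR 10/10%) or at least 2 of 9 (target 35% against 10%; stated 20/20%). With X1 ~ Bin(5, p) and X2 ~ Bin(4, p), the success probability is the sum over x1 ≥ 1 of P(X1 = x1) × P(X2 ≥ r − x1).

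- At p = 0.10: P(X1 = 1) = 0.32805, P(X1 = 2) = 0.0729, P(X1 ≥ 3) = 0.00856, P(X2 ≥ 1) = 0.3439, P(X2 ≥ 2) = 0.0523.
- r = 3: FPR = 0.32805 × 0.0523 + 0.0729 × 0.3439 + 0.00856 = 5.1%. If 2 of 5 at stage 1 already counts as success: 0.32805 × 0.0523 + 0.08146 = 9.9%. FNR at p = 0.50 is 10.0% and 8.0% respectively.
- r = 2: FPR = 0.32805 × 0.3439 + 0.08146 = 19.4%. FNR at p = 0.35 is 17.2%.

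Read as rounded upper limits, the stated rates are reproduced. They apply to whatever definition of response the 10% and target rates refer to, and the documents do not say which that is. Under protocol 8.3.2.1 a response is a confirmed one. Counting confirmed responses needs no change in sample size.

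**2. Direction of the difference.** Every confirmed responder is also a responder regardless of confirmation. On the same denominator the SAP's ORR is therefore at least the protocol's.

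**3. Size per unconfirmed response.**

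- In a cohort of 9: 1/9 = 11.1 points. At the stage 1 count of 5: 1/5 = 20.0 points.
- The Clopper-Pearson 95% limits are the 0.025 quantile of Beta(x, n − x + 1) and the 0.975 quantile of Beta(x + 1, n − x). For 2/9 = 22.2% the interval is 2.8 to 60.0. For 3/9 = 33.3% it is 7.5 to 70.1.
- The stage 2 futility and efficacy boundaries (2/3 and 1/2) are one response apart. One unconfirmed response could move a cohort across, if that is the count compared. At stage 1, one such response moves a cohort from 0 of 5 to 1 of 5 and past the futility boundary.

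**4. Can routine scans confirm?** Scan windows are anchored at first dose, so the variation of two successive scans adds.

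- Every 8 weeks ± 7 days: 56 ± 14 = 42 to 70 days apart.
- Every 9 weeks ± 7 days (Part 1 Schedules B and C): 63 ± 14 = 49 to 77 days.
- Every 12 weeks ± 7 days (Part 1, after a year on study): 84 ± 14 = 70 to 98 days.
- Survival follow-up, every 12 weeks ± 2 weeks: 84 ± 28 = 56 to 112 days.

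Each spacing exceeds 28 days, so the next scheduled scan meets both the 4-week and the 2-week rule. The interval between the last on-treatment scan and the first follow-up scan was not worked out.

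**The case against.** The strongest reply is that nothing is hidden. The SAP states its rule twice with a reason, section 1 gives it authority over the protocol's statistics, and protocol 8.4.2 leaves additional efficacy detail to it. There is no formal hypothesis, ORR is secondary, no cohort stops for efficacy, and SAP 2.1 rests enrollment decisions on a comprehensive assessment. With at most 9 subjects per cohort, the listing of tumor evaluations by visit and the swimmer plot would let a careful reader see which responses lasted. Boundaries one response apart are a feature of any final-stage cut. Parts of the SAP are redacted, and the Data Presentation Plan is not public.

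Most of this stands as a limit on impact. It does not remove the conflict: authority to supersede comes with the undertaking to identify differences, and a listing is not the endpoint.

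Two narrower points also stand. For the two lymphoma cohorts (DHL and non-GC-DLBCL), Appendix 9 as reproduced contains no confirmation rule, so the conflict there rests on protocol 8.3.2.1 alone. The DOR point has little reach in Part 2: more than five responders among 9 means at least 6/9 = 67%, above every target ORR.

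A further objection is that using confirmed counts against Table 5.2-1 presumes that the historic and target rates are confirmed rates. The documents do not say so, but the protocol's own ORR definition is the natural reading.

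**Conclusion.** The concern holds and should be fixed. As written, the SAP produces an ORR that is not the protocol's secondary endpoint and can only equal or exceed it. The summary tables described would not show the gap. Each unconfirmed response is worth 11.1 points in a cohort of 9. How often that occurs cannot be sized, because the documents give no rate of unconfirmed response.

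No controlled error rate is broken, and the consequences are those of a secondary endpoint in a design that only guides decisions. The conclusion assumes the same denominator for both versions of ORR and rests on the visible SAP text. The mismatch in DOR wording between SAP 4.2.1 and 7.5 is a minor, separate inconsistency.

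**What to change.** In SAP 4.2.1 and 7.5:

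1. Derive confirmed BOR from the recorded time-point responses by protocol 8.3.2.1, using sections 2.3.3 and 2.3.4 of Appendices 4 and 12 for solid tumors and prostate cancer. Make confirmed ORR the main summary and state that it is the count compared with Table 5.2-1.
2. Keep ORR regardless of confirmation as a supportive summary, labelled as a departure from protocol 8.3.2.1.
3. Define DOR on confirmed responders and use the threshold of more than five confirmed responses in both sections.

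The cost is SAP wording and one derived variable. Tumor evaluation at each visit is already to be listed, and the DOR threshold in 7.5 already presupposes confirmed status. No extra scan is required.

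There are downsides. The reported ORR may be lower. Some responders will lack a confirming scan, in a number the documents do not allow to be estimated. A stage 1 reading on confirmed responses comes about one scan interval later (42 to 70 days in Part 2), although SAP 5.2 allows enrollment to continue meanwhile.
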